9.2. Attrition Assumptions

We conducted power calculations prior to confirmation of the final list of participating councils. When doing this, we considered the following scenarios:

Scenario A (our planned main scenario) – Five LAs take part; 500 households recruited and randomised per LA, with 20% lost as post-randomisation attrition. Achieved n = 2,000.

Scenario B – as Scenario A, but the recruited sample in Batches 2 and 3 are reduced by 20% due to delivery constraints that become apparent in Batch 1. Achieved n = 1,736.

Scenario C – as Scenario A but one of the five LAs withdraws before the start of the trial. Achieved n = 1,600.

RBKC withdrew before the start of the trial (December 2024), so Scenario C will represent the expected main scenario at the time this protocol is first registered.

Scenario D – as Scenario B but one of the five LAs withdraws before the start of the trial. Achieved n = 1,388.

The attrition assumption covers participants opting their data out of the evaluation, gaps in administrative records, or participants moving out of the LA during the trial period. We expect such instances to be few, so the figure of 20% is likely to be conservative. It was arrived at by CHI early in the trial's development and has been maintained in the absence of strong evidence justifying amending it. Note that its impact is minor – adjusting assumed attrition in Scenario A from 20% to 5% changes the range of MDES from 2-7pp to 2-6pp.

9.3. Software

[figure not shown]
Power calculations were carried out using the [pwrss](#) package in R statistical software.

Table 7: Sample size calculations

		Scenario A	Scenario B	Scenario C	Scenario D
Minimum Detectable Effect Size (MDES) (pp = percentage points)		2-7pp	2-7pp	2-7pp	3-8pp
Alpha		0.05	0.05	0.05	0.05
Power		0.8	0.8	0.8	0.8
Alternative hypothesis: One-sided or two-sided		Two-sided	Two-sided	Two-sided	Two-sided
Number of households	Treatment	1,250	1,085	1,000	868
	Control	1,250	1,085	1,000	868
	Total	2,500	2,170	2,000	1,736
Expected attrition	%	20	20	20	20

Effective sample (Households)	Total	2,000	1,736	1,600	1,388 ²
----------------------------------	-------	-------	-------	-------	--------------------

Figure 3: Scenario C MDES at different levels of homelessness³

² This value is rounded down.

³ Note that we would not expect to see fewer than 50% of households identified by Xantura's predictive model becoming homeless if Xantura's model works as stated.

10. ANALYTICAL STRATEGY

10.1. Analytic Sample

The analytic sample will be all households entered into the randomisation for whom the primary outcome is available.

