6.4. Trial Flow Diagram

7. OUTCOME MEASURES

7.1. Primary Outcome

Definition

The primary outcome is a household-level binary variable indicating whether any household member is owed a relief duty as a result of a homelessness application made by or for any household member between the trial's start and the 9-month follow-up. There are two ways in which a homelessness application can result in a relief duty:

1. The application resulted in a '[relief duty](#)' being issued for that household.
2. The application resulted in a '[prevention duty](#)' which ended before the 9-month follow-up because the household or any household member became homeless.

Issuing a relief duty means the housing authority deems a household to already be homeless and accepts the duty to take reasonable steps to help the applicant secure accommodation. Issuing a prevention duty means the housing authority deems a household at risk of homelessness and accepts the duty to take reasonable steps to help prevent that. Those found to be homeless at the end of a prevention duty are consequently owed a relief duty.

Why is it measured

To determine whether the intervention achieves its ultimate aim of reducing homelessness among the target population.

Data source

Aggregated from Homelessness Case Level Information Classification ('H-CLIC') records, via the OneView platform.

When is it measured

At the 9-month follow-up.

For whom is it measured

All households enrolled in the trial.

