7.2. Secondary Outcomes

The trial's secondary outcomes are focused on evidence of more proximate impact of treatment on support delivered by LAs to at-risk households. Our three (binary) secondary outcome measures of support are listed below. We will consider each at

the end of the trial (i.e., the 9-month follow-up) but also at an earlier 2-month follow-up to produce evidence of early impact on an interim basis.

Secondary outcome 1: 'Prevention Duty'

Definition

Whether a [prevention duty](#) was issued to the household or any household members (1) or not (0).

Why is it measured

To indicate whether the intervention leads to increased preventative action taken by LAs, either as a result of the call making households' need for support apparent to LAs or by resulting in earlier access to support.

Data source

Aggregated from Homelessness Case Level Information Classification ('H-CLIC') records, via the OneView platform.

When is it measured

At the 9- and 2-month follow-ups.

For whom is it measured

All households enrolled in the trial.

Secondary outcome 2: 'Council tax reduction agreement' (assuming that Xantura will be able to make this data available to us)

Definition

Whether a Council Tax reduction has been agreed for the household (1) or not (0).

Why is it measured

To indicate whether the intervention leads to improved debt management support to keep at-risk households in their current accommodation.

Data source

SHBE (Single Housing Benefit Extract) data held by LAs, via the OneView platform.

When is it measured

At the 9- and 2-month follow-ups.

For whom is it measured

All households enrolled in the trial.

Secondary outcome 3: 'Discretionary Housing Payment'

Definition

Whether a Discretionary Housing Payment was issued to any household members (1) or not (0). A discretionary housing payment is a payment designed to cover housing costs for a rent shortfall, rent deposits, or to pay rent in advance if the individual needs to move home. To be eligible, individuals must receive either Housing Benefit or the housing element of Universal Credit.

Why is it measured

To indicate whether the intervention leads to improved financial support to keep at-risk households in their current accommodation.

Data source

Revenues and Benefits records held by LAs, via the OneView platform.

When is it measured

At the 9- and 2-month follow-ups.

For whom is it measured

All households enrolled in the trial.

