10.4. Secondary analyses

Our secondary analyses will follow the same approach as the primary analysis but replacing the outcome measure with the three specified secondary outcome measures:

- Whether a prevention duty was issued to any household members (1) or not (0)
- Whether a Council Tax reduction was issued to any of household members (1) or not (0)
- Whether a Discretionary Housing Payment was issued to any household members (1) or not (0)

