10.9. Interim Analyses and Data Monitoring (If applicable)

We will run the specified secondary analyses on data collected at the 2-month follow-up.

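### The only analytic sample is tied to the 9-month primary outcome and is not restated for the secondary outcomes or the 2-month analysis (minor)

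*Protocol*

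**What the plan says.** Protocol section 10.1 consists of one sentence: "The analytic sample will be all households entered into the randomisation for whom the primary outcome is available". No other analytic sample is defined in the document.

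Section 7.1 times the primary outcome "At the 9-month follow-up" only and takes it from H-CLIC records. Section 7.2 times each of the three secondary outcomes "At the 9- and 2-month follow-ups" and says of each that it is measured for "All households enrolled in the trial". Prevention duty also comes from H-CLIC. Council Tax reduction comes from SHBE, and Discretionary Housing Payment from Revenues and Benefits records.

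Section 10.4 states: "Our secondary analyses will follow the same approach as the primary analysis but replacing the outcome measure with the three specified secondary outcome measures". Section 10.9, under the interim-analysis heading, adds: "We will run the specified secondary analyses on data collected at the 2-month follow-up". Section 7.2 gives the purpose of the early look: "but also at an earlier 2-month follow-up to produce evidence of early impact on an interim basis".

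Section 10.8 describes missingness for every primary and secondary outcome, applies its 5% complete-case threshold to either kind, and allows missing outcomes to be imputed in some circumstances. Section 10.2 reports sample size and attrition separately at the start, at 2 months and at 9 months.

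**The concern.** A sample defined by availability of the primary outcome suits the primary analysis. Carried over unchanged to the secondary analyses, it has two unwanted effects.

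First, it leaves out usable data. A household with complete SHBE or Revenues and Benefits data but a gap in H-CLIC would be excluded from the Council Tax and Discretionary Housing Payment analyses. A household with complete 2-month data that then moves out of the authority would be excluded from the 2-month analyses.

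Second, it selects the 2-month sample on an event after randomisation and after the 2-month measurement. Section 9.2 counts moving out of the authority as attrition. Section 7.2 says a Discretionary Housing Payment can fund a deposit or advance rent for a move, and section 5.1 hypothesises that treatment increases these payments. Loss between months 2 and 9 could therefore differ by arm. Nothing in the protocol shows that it will, but the 2-month estimate has no need to carry that risk.

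There is also a reproducibility cost: two analysts could defend different secondary populations, one from 10.1 and one from 10.8.

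**Working it through.** **Which population each section implies**

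| Section | What it implies for a secondary analysis |
|---|---|
| 10.1 | Randomised, with the 9-month primary outcome available |
| 10.4, 10.9 | Same approach as the primary, outcome swapped, at 9 and 2 months; no population named |
| 10.8 | Complete cases on the outcome being analysed, or imputation |
| 10.2 | Sample size reported separately at 2 and 9 months |

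Sections 10.1 and 10.8 differ for any household with a secondary outcome observed and the primary outcome missing. They also differ where 10.8 imputes a missing primary outcome, since 10.1 has already excluded that household.

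**Timing (Table 5).** Secondary data for the 2-month point are pulled in August, September and October 2025. Primary outcome data are pulled in February, March and April 2026. Analysis and reporting run from May to October 2026. When the 2-month data arrive, no household has a 9-month outcome, so the 10.1 sample cannot be identified. From the last pull in April 2026 it can.

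**Reproducing the plan's figures.** Scenario C in Table 7: 2,000 × (1 − 0.20) = 1,600, or 800 per arm. Solving the two-proportion power equation (two-sided alpha 0.05, power 0.80) for the difference gives 6.98 percentage points at a 50% base rate and 1.97 for a reduction from 3%. This agrees with the stated 2-7pp. The power figures are not in error on this point.

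**Size of the possible loss**

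Inputs:
- Randomised households in the secondary analyses: 3 × 500 = 1,500. The target of 500 per authority is in section 6.2, and section 5.2 excludes Test Valley from the primary and secondary analyses. That the three authorities reach 500 each is an assumption.
- a = share missing the primary outcome. Section 9.2 plans on 20% and calls this likely conservative; it also tries 5%.
- s = share of that loss in which the secondary outcome is nevertheless observed. The protocol does not give it, so it is varied; 0.5 is illustrative only.

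Households left out although their secondary outcome is held = 1,500 × a × s.

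Ratio of standard errors, 10.1 sample against per-outcome sample = sqrt[(1 − a(1 − s)) / (1 − a)]. With s = 1 this is 1/sqrt(1 − a).

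| a | s | Left out | Ratio |
|---|---|---|---|
| 0.20 | 1 | 300 | 1/sqrt(0.80) = 1.118 |
| 0.20 | 0.5 | 150 | sqrt(0.90/0.80) = 1.061 |
| 0.05 | 1 | 75 | 1/sqrt(0.95) = 1.026 |
| 0.05 | 0.5 | 37.5 | sqrt(0.975/0.95) = 1.013 |
| any | 0 | 0 | 1 |

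In minimum detectable difference at a 50% base rate, with s = 1: at a = 0.20 the 10.1 sample of 1,200 gives 8.05pp against 7.21pp for all 1,500; at a = 0.05 the sample of 1,425 gives 7.40pp against 7.21pp.

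The fraction s should be larger for the 2-month outcomes, where any loss after month 2 counts, than for the 9-month outcomes, where a data opt-out or a move is likely to remove everything together.

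**The case against.** The strongest reply is that 10.1 is loosely worded and the rest of the plan already treats each outcome separately. Section 10.4 swaps the outcome, and it is natural for availability to follow the outcome analysed. Section 10.8 speaks of missingness in primary and secondary outcomes alike, by arm, and section 10.2 reports a sample size at 2 months. Analysis sets by outcome are also often left to a statistical analysis plan. Much of this stands, and it rules out saying that the plan orders secondary data to be discarded. What remains is that 10.1 states a rule, nothing limits it to the primary analysis, and following it gives a worse result than following 10.8. That is a conflict in the protocol's own text, not detail deferred to another document.

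A reader might infer more than the text supports in four ways:

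- **That the 2-month analysis cannot be run.** This holds only if it is run when its data arrive. The sections call it interim but give no analysis date, and Table 5 puts analysis after the 9-month data are in.
- **That section 7.2 sets a different analysis population for the secondary outcomes.** Its statement concerns whom the outcome is measured for, and section 7.1 says the same of the primary outcome.
- **That there will be two conflicting 2-month estimates, interim and final.** No second 2-month estimate is planned.
- **That 300 households will be lost.** A data opt-out removes every outcome, a move is likely to affect all 9-month authority records together, and prevention duty shares H-CLIC with the primary outcome. Section 10.8 expects little missing data overall.

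**Conclusion.** The point holds as a minor inconsistency. Section 10.1 fixes a single sample by availability of the 9-month primary outcome; the secondary and 2-month analyses inherit it by default, and section 10.8 points to a different population. Taken literally, 10.1 excludes some households with observed secondary outcomes and conditions the 2-month results on loss up to month 9.

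The effect on precision lies between nothing and a ceiling of a 12% rise in standard errors; at 5% missing it is at most 2.6%. Both upper figures assume that all loss is specific to the primary outcome, and the household counts assume 1,500 randomised in the three analysed authorities. The likely effect is small. The direction and size of any selection bias at 2 months cannot be derived from the protocol. The primary analysis and the stated power are unaffected.

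**What to change.** Replace the sentence in section 10.1 with: *For each outcome and time point, the analytic sample is all randomised households, in the arm assigned, with that outcome observed at that time point.* Refer to this definition in sections 10.4 and 10.9. In section 10.8, state that complete-case analysis uses this sample and that the imputation analyses extend it. Report n by arm for every outcome and time point; section 10.8 already plans missingness by arm, so this adds little work.

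The primary complete-case sample does not change. The only cost is that denominators will differ slightly between outcomes and time points, which the reported counts make plain.

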10.2. Descriptive statistics

We will report descriptive statistics on:

- Sample size and attrition at the trial's start, the 2-month follow-up, and the 9-month follow-up
- Predicted baseline risk scores across arms at the trial's start, the 2-month follow-up, and the 9-month follow-up (to assess balance)
- Variables for underlying risk factors used to develop the predicted baseline scores
- The primary outcome at the 9-month follow-up (the full distribution as well as summary statistics – mean, mode, standard deviation)
- All secondary outcomes at the 2-month and 9-month follow-ups
- Whether and when treatment arm households received the call
- Whether and when households were issued a prevention duty
- Whether and when households were issued a relief duty

10.3. Primary Analyses

Analytical approach

The primary analysis will estimate the effect of treatment on the likelihood of a successful homelessness application being submitted by or on behalf of any individual within a sampled household, on an intent-to-treat (ITT) basis. We plan to apply a parsimonious model with treatment as the predictor of interest, and two baseline covariates used in the blocking design of the randomisation.

The analysis will take the form of a generalised linear model with a logit link function to accommodate the binary measure used for the primary outcome. To improve power, we will cluster standard errors at the block level.

The model will follow this specification:

$$\text{logit}(p(Y_i = 1)) = \beta_0 + \beta_1 \text{Treat}_i + \beta_2 \text{Risk}_i + \beta_3 \text{LA}_i$$

Where:

- $p(Y_i = 1)$ is the probability that the i^{th} household ($i = 1, \dots, n$, where n is the number of households) submitted a successful homelessness application (or had one submitted on their behalf) during the trial period,
- $Treat_i$ is a binary variable for treatment allocation (0 = Control, 1 = Intervention),
- $Risk_i$ is the continuous risk score generated for that household that was used in the pre-trial randomisation,
- LA_i is a vector of binary dummy variables representing the Local Authority the household is in (0 = non-member, 1 = block member).

This approach to the primary analysis cleanly reflects the study's design to maximise power without conditioning on additional covariates that could complicate the interpretation of the model's results. Alternative approaches would be to explicitly represent the blocking design through a vector of dummy variables (instead of separate indicators for risk and LA) in a conditional logistic regression or to drop all covariates and use treatment as the sole predictor. We will follow both of these approaches as sensitivity analyses.

We will report uncertainty through confidence intervals at p-values. For the treatment effect, we will report p-values continuously as well as a binary indication of whether the treatment effect is statistically significant.

10.4. Secondary analyses

Our secondary analyses will follow the same approach as the primary analysis but replacing the outcome measure with the three specified secondary outcome measures:

- Whether a prevention duty was issued to any household members (1) or not (0)
- Whether a Council Tax reduction was issued to any of household members (1) or not (0)
- Whether a Discretionary Housing Payment was issued to any household members (1) or not (0)

10.5. Sub-group Analyses

There are no planned sub-group analyses apart from an exploration of differential impact across LAs, which is set out under Exploratory Analyses.

10.6. Sensitivity Analysis

Alternative analysis methods

To test the robustness of the trial's main findings to different analysis methods, we will repeat the primary analysis introducing several variations.

Firstly, we will re-run the primary model using a probit link function instead of a logit, per CHI's Statistical Analysis guidance. This analysis tests whether the trial's results hold under an alternative and equally justifiable approach to that taken in the primary analysis.

Secondly, we will trial an alternative analysis in which the indicators for LA and baseline risk are replaced with a vector of dummy variables representing the blocks to which households were assigned. This analysis would be a conditional logistic regression, which is better suited to handling many small strata that do not gain precision as the study's sample size increases (since the stratum size remains constant at 4 households). This analysis captures the impact of treatment in the event that predicted risk scores vary in predictive power across LAs.

And thirdly, we will repeat the main analysis but dropping all predictor variables apart from treatment. This approach is likely to lose power, but if in practice the baseline risk scores of households recruited into the trial are generally high and with little variation, then the loss may be minimal. We will run this analysis both including and excluding cases from Test Valley.

Compliance analysis (CACE)

To complement the primary ITT analysis, we will also conduct Complier Average Causal Effect (CACE) analysis to provide a more accurate measure of treatment efficacy amongst 'compliers'. We will apply the instrumental variables approach using the Two Stage Least Squares (2SLS) method.

For a household in the treatment arm to be considered 'compliant', the following must be true:

- The LA call handler successfully made telephone contact with an adult member of the household
- They were able to complete the treatment call (i.e., they were not cut off prematurely)
- If any member of the household submitted a homelessness application within the trial period, the call took place before that application was made.

This definition does not consider whether household members were sent a text message because the purpose of that part of the intervention is solely to increase uptake of the calls, which is directly measured by the compliance indicator. That means a household who received the call but not the text message would still be considered fully compliant, while one who received the message but not the call would be considered non-compliant.

Our measure of compliance will be a binary indicator; set to 1 if all of the above are true, or otherwise set to 0. First, this indicator is regressed on the variable indicating random assignment to treatment at the trial's start (the instrument). The resulting model predicts treatment received based on allocation to arm, which is then substituted in the primary analysis model for the variable representing allocation to treatment.

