Call handlers will be given a group training session on how to use the telephone guidance pack. Call handlers will also be asked to rely on their prior training and experience when making the calls and navigating potentially challenging conversations. LAs may also provide project-specific training to call handlers, but this is at the LA's discretion. The call handlers making outreach calls to residents will come from existing LA teams with expertise in making outreach calls. The subject knowledge of teams might differ across LAs, but at a minimum all teams will have experience and training in outreach activities.

The intervention, a call to proactively signpost households in need to support services, is deemed to have been delivered in full once the call handler considers that they have made an appropriate assessment of the household's (and/or individual's) needs and indicates that on the OneView platform. Call handlers will be instructed to confirm with participants that they understand what was discussed in the call, following the guidance document provided for the calls (see Annex B: Call Guidance for Local Authorities). Call handlers will also direct households to appropriate services (either by sharing the service's phone number or making a referral and having services contact households directly).

If the call handler judges they are required, follow-up calls may be made over a maximum period of 6 months. This is likely to be needed if participants are unable or unwilling to complete the assessment on the first call made (e.g. due to lack of time), but they do not decline further calls from the LA. Therefore, the length and number of calls will vary according to the risks/needs identified. Detailed call records will be maintained via the OneView platform.

The project relies on LA staff to make outreach calls and adhere to the guidance about the content of the calls. We will ask the managers of teams making the calls to conduct spot checks with all call handlers by shadowing random calls on a regular basis (at least weekly), check the call follows the guidance appropriately, and report

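### The complier analysis is named 2SLS but specified with a logistic second stage, so it returns the ITT log-odds ratio divided by the compliance rate, which is not in general the complier effect

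*Protocol*

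**What the plan says.** Protocol Section 10.6 (Compliance analysis) says of the method: "We will apply the instrumental variables approach using the Two Stage Least Squares (2SLS) method". The aim is to "provide a more accurate measure of treatment efficacy amongst" compliers. The steps follow. "First, this indicator is regressed on the variable indicating random assignment to treatment". The fitted value is the prediction "which is then substituted in the primary analysis model for the variable representing allocation to treatment". Section 10.3 describes the primary model thus: "The analysis will take the form of a generalised linear model with a logit link function", with treatment, risk score and LA as predictors.

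Compliance is defined only for the intervention arm ("For a household in the treatment arm to be considered" compliant, three conditions apply). An adult in the household must have been reached by telephone. The call must have been completed. Any homelessness application must have come after the call. Every other household is coded 0.

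**The concern.** Least squares and a logit model are different second stages, so the method named and the method described cannot both be followed. Followed literally, the description substitutes a predictor into a non-linear model, which does not recover the complier effect in the way that 2SLS does for a risk difference.

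This is the only planned quantitative estimate of the effect among households actually reached. If many households cannot be reached, readers will turn to it to interpret a diluted ITT result.

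A smaller, related matter is the coding of exposure. Calls that were cut off, and calls made after an application, count as no exposure. The division by the compliance rate then assumes that such calls have no effect at all.

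**Working it through.** **Inputs.** The protocol gives no figure for the CACE and no expected compliance rate. For illustration I use the contact rate of the earlier Barking and Dagenham exercise in Section 1.1, 68/210 = 0.324, as the compliance rate c. It is a reach rate from another campaign, so it is an assumption here.

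**Scale of effect.** The protocol's related figure is its MDES of 2-7 percentage points (Table 7, Scenario C, 1,600 households). At 800 per arm, two-sided alpha 0.05, power 0.80 and risks 50.0% and 43.02%: (1.96 × √(2 × 0.4651 × 0.5349) + 0.8416 × √(0.2500 + 0.2451)) / √800 = 0.0698, or 6.98 points, which matches the upper end. A complier effect of -20 points at c = 0.324 is an ITT effect of -20 × 0.324 = -6.48 points, close to that upper end.

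**What the written procedure returns.** With compliance 0 in controls, a first stage on assignment alone gives a fitted value of c × Treat. Replacing Treat by c × Treat in the logit model gives a coefficient of β(ITT)/c, with the ITT p-value. A simulation (300 trials per scenario, 1,200 households in blocks of four) confirmed this to within 1e-13.

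**Planned against true complier odds ratio.** The mixture below ignores covariates. Arm risk = c × complier risk + (1 - c) × other risk. Planned OR = exp(ln(ITT OR)/c). The complier effect is -20 points throughout.

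| c | Control risk, compliers / others | ITT OR | Planned OR | True complier OR | Error in log-OR |
|---|---|---|---|---|---|
| 0.324 | 50% / 50% | 0.771 | 0.447 | 0.429 | 5% too small |
| 0.324 | 60% / 50% | 0.771 | 0.449 | 0.444 | 1% too small |
| 0.324 | 70% / 70% | 0.746 | 0.405 | 0.429 | 7% too large |
| 0.324 | 40% / 55% | 0.771 | 0.447 | 0.375 | 18% too small |
| 0.60 | 40% / 55% | 0.605 | 0.433 | 0.375 | 15% too small |

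Worked for the fourth row: control 0.324 × 0.40 + 0.676 × 0.55 = 0.501; treated 0.324 × 0.20 + 0.676 × 0.55 = 0.437; ITT OR 0.771; ln = -0.261; divided by 0.324 = -0.804; exp = 0.447. True OR = (0.20/0.80)/(0.40/0.60) = 0.375.

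Rows one and four have the same ITT OR and the same c but different true complier ORs. The complier OR is therefore not a function of those two quantities. The risk difference is: -6.48/0.324 = -20.0 points in every row with c = 0.324.

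Over the range 50-70% for both risks, c from 0.32 to 0.60 and complier effects of -10 or -20 points, the error in the log-OR runs from about -9% to +9%.

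**Linear 2SLS in the same simulation.** Average estimate against truth: -21.6 against -21.2, -21.3 against -21.7, and -11.2 against -11.7 points.

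**Exposure coding.** Suppose a share s of real contacts is coded 0 and benefits as much as the rest. The effect per contacted household is then overstated by 1/(1 - s): 1.11 at s = 10% and 1.25 at 20%. If those contacts benefit half as much, the factors are 1.06 and 1.13. If they do not benefit, there is no bias. The protocol gives no value for s.

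**The case against.** The strongest reply is that the CACE only complements the ITT analysis, and that the error is small where the protocol expects to be. Section 6.1 admits households with a score of at least 50, read as expected likelihood of homelessness. The footnote to Figure 3 expects no fewer than 50% to become homeless. On that expectation the error stays within about 9%. This stands, and it limits the importance of the point. It does not remove it: Section 9.1 concedes that little is known about how well the scores predict homelessness, and Section 15.2 lets LA staff decide which listed households to call, so equal complier and non-complier risk cannot be presumed.

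A reader might infer more than the document supports:

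- **That dividing by c is itself the fault.** Linear 2SLS does the same to the risk difference, and validly. The fault lies in dividing a log-odds ratio.
- **That the error typically reaches 40%.** That needs complier risk of 30% against 60% in others, an invented contrast that conflicts with Section 6.1.
- **That the confidence interval and p-value are materially wrong.** Ignoring uncertainty in c (first order, no covariance) changes the SE by √(1 + z²(1 - c)/(nc)). With c = 0.324, that is 0.5% at n = 800 treated and z = 2, and 1.4% at n = 600 and z = 2.8. With one instrument, the test of no complier effect is in substance the ITT test.
- **That calls after the first month are lost because Table 6 lists one intervention month.** Section 3.1 allows that "follow-up calls may be made over a maximum period of 6 months" and keeps call records in OneView. The compliance definition has no one-month limit.
- **That the compliance definition should be replaced.** It follows Section 3.1, where delivery is complete only once needs have been assessed. Counting any contact up to nine months would include households first reached after the outcome had occurred.

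**Conclusion.** Wrong as written, of secondary importance. Sections 10.3 and 10.6 together specify an estimator that is not the 2SLS they name and does not in general estimate the complier effect. The result that it equals the ITT log-odds ratio divided by c follows from the text alone. The size of the error does not. It is within about 9% if both groups' risks are 50-70%. It is 18% on the log scale (OR 0.45 against 0.375) in the assumed scenario of 32% compliance, risks of 40% and 55%, and a -20 point effect. The primary ITT estimate, its p-value and the power calculation are untouched.

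The exposure coding deserves a check, not a change of main definition. Section 15.2 accepts that part of the intervention has been given when someone declines during a call. A call made after an application could still affect the second outcome route in Section 7.1, a prevention duty that ends in homelessness. If such calls help, coding them 0 inflates the estimate. The documents show neither how often they occur nor whether they have an effect, so no particular inflation factor can be claimed.

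**What to change.** In Section 10.6, replace the substitution into the primary model with linear 2SLS. Regress the outcome on compliance, instrumented by assignment, with Risk and LA in both stages and standard errors clustered by block. Report the complier risk difference in percentage points with its 2SLS confidence interval. Using Risk keeps the sample to that of the primary analysis, without Test Valley (Section 5.2).

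Keep the stated compliance definition as the main one. Add one sensitivity analysis that counts any telephone contact with an adult household member as exposure, and note that it may include contacts made after the outcome.

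The cost is a short wording change, recorded as an addendum under Section 13.2 before analysis begins (May 2026 in Table 5), and one standard instrumental-variables command. No new data are needed: Section 11.2 already lists contact made and call completed among the items recorded in OneView.
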